1.2. Schema

1.3. Schedule of Activities

The SoA tables provide an overview of the protocol visits and procedures. Refer to the [STUDY ASSESSMENTS AND PROCEDURES](#) section of the protocol for detailed information on each assessment required for compliance with the protocol.

The investigator may schedule visits (unplanned visits) in addition to those listed in the SoA table, in order to conduct evaluations or assessments required to protect the well-being of the participant.

090177e198aafefApproved\Approved On: 22-Nov-2021 20:52 (GMT)

Table 1. Schedule of Activities (Part 1 and Part 2)

Visit Identifier	Screening	28 Day Treatment Cycle					EOT	30 day safety F/U	Long-term safety F/U	Notes:
		Day 1	Day 2	Day 8	Day 15	Day 22				
Abbreviations used in this table may be found in Appendix 17 .	≤28						See notes	See notes		
 EOT and 30-day F/U see Sections 8.2.8 and 8.2.9 for timing of visits. See Section 8.2.9 for 60- and 90-day F/U. See Section 8.3.3 for follow-up AE and SAE assessments.
Visit Window (Days)		±2	—	±1	±1	±1		±3	±7	No Visit Window for C1D1. A 2-day Visit Window for Day 1 starts with Cycle 2.
Informed consent	X									Informed consent must be obtained prior to undergoing any study specific procedures.
Registration	X									Participant enrollment number and dose level allocation assigned by Pfizer Inc.
Demographics & medical history	X									Includes history of the cancer under study and any other relevant medical/surgical history.
Complete physical examination	X						X			
Brief physical examination		X	C1	C1 & C2	X	C1		X		
Height		C1								
Weight		X					X			
Vital signs	X	X	C1	C1 & C2	X	C1	X	X		See Section 8.2.3 For additional information.
ECOG performance status	X	X	C1	C1 & C2	X	C1	X	X		See Section 8.2.2 and Section 10.14 for additional information.
Contraception check		X					X			

090177e198aafefApproved On: 22-Nov-2021 20:52 (GMT)

Table 1. Schedule of Activities (Part 1 and Part 2)

Visit Identifier	Screening	28 Day Treatment Cycle					EOT	30 day safety F/U	Long-term safety F/U	Notes:
		Day 1	Day 2	Day 8	Day 15	Day 22				
Abbreviations used in this table may be found in Appendix 17 .	≤28						See notes	See notes		
 EOT and 30-day F/U see Sections 8.2.8 and 8.2.9 for timing of visits. See Section 8.2.9 for 60- and 90-day F/U. See Section 8.3.3 for follow-up AE and SAE assessments.
Visit Window (Days)		±2	—	±1	±1	±1		±3	±7	
Laboratory Assessments										

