2.3. Benefit/Risk Assessment

Since this is the FIH study, no human studies have been conducted to date evaluating PF-07265028. For selected disease indications where effective treatment options are not available, the benefit/risk relationship has been carefully considered in the planning of this trial based on pre-clinical, toxicology studies and nonclinical safety profiles of PF-07265028.

Safety findings with PF-07265028 that were observed in the nonclinical studies include: gastrointestinal toxicity, reductions in lymphocytes in blood and secondary lymphoid tissues and increases in blood pressure/heart rate. During this Phase 1 study, clinical assessments will include frequent safety monitoring. The participants will be monitored during and for at least 7 hours following their first dose. This will be implemented throughout dose escalation. In Japan, the participants will be monitored during and following their first dose with at least 24-hour inpatient hospitalization period. When a participant is discharged from the hospital during the DLT evaluation period, the conditions (tests, medical examinations, etc) described should be performed on the day of the scheduled discharge by the investigators, and the propriety of discharge should be determined. This will be implemented throughout dose

escalation and length of inpatient hospitalization will be re-assessed based on safety data prior to starting dose expansion cohorts).

More detailed information about the known and expected benefits and risks and reasonably expected AEs of PF-07265028 may be found in the PF-07265028 IB, which is the PF-07265028 SRSD for this study.

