2.3.1. Risk Assessment

Potential risks of clinical significance for sasanlimab are provided in the sasanlimab IB.

Study Intervention: PF-07265028

Potential Risk of Clinical Significance	Summary of Data/Rationale for Risk	Mitigation Strategy
Immune-related toxicity	The potential overlapping risks are based on the sasanlimab IB and nonclinical studies for PF-07265028.	
 Guidelines for treatment interruption/dose reductions and discontinuation in case toxicities, and guidelines for steroid treatment implementation are incorporated in Section 6.5.1.
ISRs	The potential risks of sasanlimab administered with PF-07265028 are based on the sasanlimab IB and nonclinical studies for PF-07265028.	
 Participants should be monitored for serious and nonserious AEs, including ISRs, following administration of sasanlimab (in Parts 1B and 2A). When appropriate, at the discretion of the investigator, a participant with an ISR may be referred for a dermatological consultation and skin biopsy may be obtained for future examination of the ISR. If injection site reaction is noted, site tolerability assessments should continue until the symptoms resolve. Refer to Section 8.2.7.
Gastrointestinal (mucosal erosion, epithelial degeneration/regeneration) with accompanying clinical signs of emesis and diarrhea.	The potential risks are based on nonclinical toxicology data for PF-07265028 in mice and monkeys.	
 Participants will be monitored for gastrointestinal toxicity. At the discretion of the investigator therapeutic and prophylactic supportive care may be considered. Dose reductions/ interruptions and discontinuations are permissible. Potential of dosing with food.
Marrow (increased myeloid to erythroid ratio)	The potential risks are based on nonclinical toxicology data for PF-07265028 in mice and monkeys.	
 Participants will be monitored for hematologic toxicity. At the discretion of the investigator therapeutic and prophylactic supportive care may be considered. Dose reductions/ interruptions and discontinuations are permissible.
Increased hemodynamics (increased heart rate and/or blood pressure)	Identified in a single dose cynomolgus monkey telemetry study of PF-07265028.	
 Participants will have serial vital signs performed.

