6.1.1. Administration

6.1.1.1. PF-07265028

Participants will swallow PF-07265028 tablets whole with at least 8 ounces (240 mL) of water, and will not manipulate or chew the study intervention prior to swallowing. PF-07265028 will initially be administered QD by mouth for all cohorts on a continuous basis. Participants who are unable to swallow whole tablets may dissolve their dose in oral syringe(s) as outlined in the IP manual to allow for suspension administration either orally or via an NG tube. If supported by emerging data, BID continuous regimen may be considered. A cycle is defined as 28 days, regardless of missed doses or dose delays.

Participants will take PF-07265028 at approximately the same time within each dosing interval (ie, ± 3 hours of nominal time). On site visit days, participants will take the drug at the site after performing predose assessment. On other days, participants will be instructed to self-administer the drug at home. A dosing diary will be given to each participant to support at home dosing. The participants will be requested to note the date and time of each dose, food consumption status at the time of drug administration.

If a participant misses a dose at the scheduled time, the participant can still take the dose within 4 hours of the scheduled time. If the participant missed taking a dose after 4 hours of the scheduled time, or day of treatment, they must be instructed not to “make it up” but resume subsequent doses as prescribed. This dose will be considered as a missed dose. In addition, if a participant vomits any time after taking a dose, they should not “make it up” but to resume subsequent doses as prescribed. Lastly, if a participant inadvertently takes 1 extra dose during a day, the participant should not take the next dose of PF-07265028.

Food Requirements (Except for the Food-Effect Subset or Cohorts Evaluating Food Intake on Tolerability)

Participants will take PF-07265028 orally with at least 8 oz (240 mL) of water on an empty stomach. No food or liquids other than water will be consumed for 2 hours before and 2 hour following each dose throughout the study).

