8. STUDY ASSESSMENTS AND PROCEDURES

The investigator (or an appropriate delegate at the investigator site) must obtain a signed and dated ICD before performing any study-specific procedures.

Study procedures and their timing are summarized in the [SoA](#). Protocol waivers or exemptions are not allowed.

Safety issues should be discussed with the sponsor immediately upon occurrence or awareness to determine whether the participant should continue or discontinue study intervention.

Adherence to the study design requirements, including those specified in the [SoA](#), is essential and required for study conduct.

All screening evaluations must be completed and reviewed to confirm that potential participants meet all eligibility criteria. The investigator will maintain a screening log to record details of all participants screened and to confirm eligibility or record reasons for screening failure, as applicable.

Procedures conducted as part of the participant's routine clinical management (eg, blood count) and obtained before signing of the ICD may be utilized for screening or baseline purposes provided the procedures met the protocol-specified criteria and were performed within 14 days prior to signing of the ICD.

Every effort should be made to ensure that protocol-required tests and procedures are completed as described. However, it is anticipated that from time to time there may be circumstances outside the control of the investigator that may make it unfeasible to perform the test. In these cases, the investigator must take all steps necessary to ensure the safety and well-being of the participant. When a protocol-required test cannot be performed, the investigator will document the reason for the missed test and any corrective and preventive actions that he or she has taken to ensure that required processes are adhered to as soon as possible. The study team must be informed of these incidents in a timely manner. For samples being collected and shipped, detailed collection, processing, storage, and shipment instructions and contact information will be provided to the investigator site prior to initiation of the study.

All assessments are relative to start of study intervention (Cycle 1 Day 1). All assessments to be completed prior to administration of study intervention unless otherwise noted per study visit.

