8.2.3. Vital Signs

BP and pulse rate measurements will be assessed either in the sitting position with feet supported (ie, not dangling) or the semi-recumbent/supine position. It is recommended that the same position be used consistently throughout the study duration unless circumstances, eg, hospitalization, dictate otherwise. BP should be obtained using the auscultatory method or via an automated BP device, ensuring use of an appropriately sized cuff on the bare arm and consistent technique of measurement (eg, using the same arm each time). Care should be taken to use the appropriate size BP cuff for the participant's arm circumference as incorrect cuff sizes can lead to falsely elevated BP measurements.

Abnormal readings should be repeated and confirmed.

Blood pressure and pulse rate measurements should be preceded by at least 5 minutes of rest for the participant in a quiet setting without distractions (eg, television, cell phones).

Pulse rate preferably should be obtained using a pulse oximeter, automated BP device, or other pulse measurement device.

Temperature may be determined using oral, tympanic, axillary, or temporal (ie, forehead scan) methods of measurement, as long as the chosen method is used consistently (oral preferred). The method of temperature measurement should be noted in the CRF.

When should it be done:

Vital sign assessments should precede blood draw for clinical laboratory tests.

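### The only mitigation for raised blood pressure and heart rate is serial vital signs, but the schedule sets one pre-dose set per visit and no post-dose blood pressure time

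*Protocol*

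**What the plan says.** - **The risk.** The table in Protocol Section 2.3.1 lists increased heart rate and/or blood pressure under its column of potential risks. The basis is "Identified in a single dose cynomolgus monkey telemetry study of PF-07265028". The whole mitigation is "Participants will have serial vital signs performed".
- **The schedule.** The vital-signs row of Schedule of Activities (SoA) Table 1 covers screening, Day 1 of every cycle, Day 2 (Cycle 1), Day 8 (Cycles 1 and 2), Day 15 of every cycle, Day 22 (Cycle 1), end of treatment and the 30-day follow-up. Each day has one mark and no hour. The ECG and PK rows point to the timed Tables 2 to 4. The vital-signs row says instead: "See Section 8.2.3 For additional information".
- **The procedure.** The only within-day timing rule in Section 8.2.3 is "Vital sign assessments should precede blood draw for clinical laboratory tests".
- **The default.** Section 8 states: "All assessments to be completed prior to administration of study intervention unless otherwise noted per study visit". Section 6.1.1.1 gives the same order: "On site visit days, participants will take the drug at the site after performing predose assessment".
- **First-dose observation.** Section 2.3, just after naming the blood pressure and heart rate finding, says: "The participants will be monitored during and for at least 7 hours following their first dose". This applies throughout dose escalation, and in Japan the first dose is followed by at least 24 hours in hospital. Neither statement says what is measured.
- **The analysis.** SAP Section 6.1.4 summarises on-treatment vital signs only by the abnormality categories of its Appendix 1. These include a maximum systolic pressure of 160 mm Hg or more, a maximum diastolic pressure of 100 or more, and maximum increases of at least 30 (systolic) and 20 (diastolic).

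**The concern.** The animal signal came from single-dose telemetry, so the natural question in humans is what happens to blood pressure in the hours after a dose. Read as written, the schedule puts the Cycle 1 Day 1 reading before any drug has been given and the other Cycle 1 readings about 24 hours after the previous once-daily dose.

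Two uses of the data are affected. SAP Section 6.1.4 sits under the Part 1 primary endpoints, and Section 6.4.2 counts vital signs among the Part 2 primary safety endpoints, so their maxima would be reported although no reading was required near the likely peak. Protocol Section 4.1 also allows a move to twice-daily dosing if adverse events related to peak concentration appear. Pre-dose blood pressure is poorly suited to informing that decision.

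The emphasis is also uneven. Section 2.2.7 reports hemodynamic changes but no ECG or QT change in monkeys. Yet ECGs have a 2 h post-dose time on Cycle 1 Day 15 (Tables 3 and 4), and blood pressure has none.

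**Working it through.** **Step 1: count what is scheduled.** From Table 1, the on-treatment vital-sign days are 5 in Cycle 1 (Days 1, 2, 8, 15, 22), 3 in Cycle 2 (Days 1, 8, 15) and 2 per cycle after that (Days 1, 15). Across Table 1 and Section 8.2.3, the number of post-dose blood pressure times is 0.

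**Step 2: reproduce the half-life.** Section 2.2.6 gives a clearance of 5 mL/min/kg (0.30 L/h/kg), a volume of 5 L/kg and an effective half-life of 12 h. The check is 0.693 × 5 / 0.30 = 11.55 h, which rounds to the stated 12 h.

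**Step 3: compare pre-dose with peak.** The documents give no absorption rate or Tmax, so ka = 0.3 to 2 per hour is an assumption. The model has one compartment with dosing every 24 h and k = 0.693/12 = 0.0578 per hour.

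- First dose: C(t) ∝ exp(−kt) − exp(−ka·t)
- Steady state: C(t) ∝ exp(−kt)/(1 − exp(−24k)) − exp(−ka·t)/(1 − exp(−24ka))

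Worked case, steady state, ka = 1: exp(−24k) = 0.25, so the trough is 0.25/0.75 − 0 = 0.333. The peak is at 2.72 h and equals 0.855/0.75 − 0.066 = 1.074. The ratio is 0.333/1.074 = 0.31.

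Concentration as a fraction of peak, steady state:

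| ka (/h) | Tmax (h) | Pre-dose | 2 h | 4 h | 7 h |
|---|---|---|---|---|---|
| 0.3 | 5.6 | 0.427 | 0.821 | 0.972 | 0.986 |
| 0.5 | 4.2 | 0.361 | 0.888 | 0.999 | 0.931 |
| 1 | 2.7 | 0.310 | 0.980 | 0.969 | 0.828 |
| 2 | 1.7 | 0.284 | 0.995 | 0.900 | 0.757 |

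Concentration as a fraction of peak, first dose:

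| ka (/h) | Tmax (h) | Day 1 pre-dose | 2 h | 4 h | 7 h | Day 2 pre-dose |
|---|---|---|---|---|---|---|
| 0.3 | 6.8 | 0 | 0.628 | 0.903 | 1.000 | 0.457 |
| 0.5 | 4.9 | 0 | 0.784 | 0.987 | 0.955 | 0.375 |
| 1 | 3.0 | 0 | 0.955 | 0.980 | 0.842 | 0.316 |
| 2 | 1.8 | 0 | 0.998 | 0.908 | 0.764 | 0.286 |

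The steady-state pre-dose level is therefore 28% to 43% of peak (27% to 41% with the unrounded 11.55 h), and the Day 2 pre-dose level is 29% to 46% of the Day 1 peak. A single 2 h reading reaches 82% to 100% of peak at steady state but only 63% to 100% after the first dose. With readings at 2, 4 and 7 h, the best of the three is at 98% of peak or more for every ka shown, in both settings.

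**The case against.** The other side has several fair points.

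- **First-dose monitoring.** A reader might infer that blood pressure is never measured near peak. The documents do not support that. The monitoring of at least 7 hours covers every Tmax in the tables above, and sites may well take blood pressure during it. What stands is that no measurement, time or recording is specified, that it covers the first dose only, and that it is stated for escalation. It does not secure steady-state readings or uniform data for the SAP.
- **Status of the risk.** A reader might call this an identified drug risk. The protocol lists it as a potential risk from monkeys, Section 2.2.7 calls the changes modest, and no human data exist yet.
- **Meaning of serial.** Repeated readings across visits are a fair reading of the word. Even so, none of those readings is required after a dose.
- **Heart rate.** Post-dose ECGs give heart rate, so that half of the risk is partly covered. They give no blood pressure.
- **Pre-dose timing is inferred.** It rests on the Section 8 default. Table 2 lists in-clinic dosing on Day 8 in Cycle 1 only and on Day 15 in Cycles 1 to 3 only, whereas Table 1 has vital signs on Day 8 of Cycle 2 and Day 15 of every cycle. Section 6.1.1.1 has the drug taken on site on visit days. Dose timing at those later visits is therefore unclear, and not every later reading is certain to be at trough.
- **Redaction.** Tables 2 to 4 contain blacked-out rows. However, Table 1 sends vital signs to Section 8.2.3, which is fully legible, and the titles of Tables 2 to 4 do not list vital signs.
- **Pre-dose readings carry information.** If exposure is dose-proportional (assumed), trough at 125 mg is 5 × 0.28 to 5 × 0.43 = 1.4 to 2.15 times the peak at 25 mg. Escalation could still reveal an effect, only later and less sensitively.

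**Conclusion.** The point holds as a gap in specification. The protocol relies on vital signs for a potential hemodynamic risk, and its schedule, followed as written, requires no blood pressure reading near peak concentration either on Day 1 or at steady state. The SAP's maximum values and maximum increases would then come from pre-dose readings.

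The size is a pre-dose concentration of about 28% to 43% of peak at steady state and zero on Cycle 1 Day 1. This rests on the 12 h half-life, a one-compartment model, once-daily dosing and an assumed ka of 0.3 to 2 per hour.

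Two stronger inferences should be avoided. One is that 57% to 72% of the peak effect goes unseen (100% minus 43% and 28%). That needs an effect that follows concentration immediately and linearly, which no section supports. The other is that the absence of a signal would mean nothing. Pre-dose readings are less sensitive, not uninformative. Nor is there a basis for saying that vital signs drive escalation directly: the dose model uses Cycle 1 dose-limiting toxicities, and Protocol Section 3 does not list vital signs among its primary endpoints.

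**What to change.** 1. Reconcile Protocol Sections 2.3, 2.3.1, 8 and 8.2.3 with SoA Table 1. State whether the first-dose monitoring includes blood pressure and pulse, and at which times.
2. In Table 1 and Section 8.2.3, add blood pressure and pulse pre-dose and post-dose on Cycle 1 Day 1 and Cycle 1 Day 15. In Part 1 use 2, 4 and 7 h, which are already PK times in Table 2; slow absorption could leave the 2 h level after the first dose well short of peak. In Part 2 use 2 h, the post-dose time already in Table 3.
3. Record the nominal time of each reading.
4. In SAP Section 6.1.4, summarise post-dose values separately from pre-dose values, so that the Appendix 1 maxima can be read against time since dose.

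The cost is a few extra cuff readings at visits where participants are already on site, and one row in the schedule.

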8.1. Efficacy Assessments

8.1.1. Tumor Response Assessments

Tumor assessments will include all known or suspected disease sites. Imaging will include contrast enhanced chest, abdomen and pelvis computed tomography or MRI scans; brain computed tomography or MRI scan for participants with known or suspected brain metastases; bone scan for participants with known or suspected bone metastases. For participants with known computed tomography contrast allergy, a non-contrast CT of the chest with contrast enhanced abdominal and pelvic MRI can be used. The same imaging technique used to characterize each identified and reported lesion at baseline will be employed in the following tumor assessments.

Anti-tumor activity will be assessed through radiological tumor assessments conducted at baseline, during treatment as specified in the [schedule of activities](#), whenever disease progression is suspected (eg, symptomatic deterioration), and at the time of withdrawal from treatment (if not done in the previous 4 weeks). Investigator (local) assessment of response will be made using RECIST version 1.1 and irRECIST (see [Sections 10.12](#) and [10.13](#)).

All participants' files and radiologic images must be available for source verification and for potential peer review.

8.2. Safety Assessments

Planned time points for all safety assessments are provided in [SoA](#). Unscheduled clinical laboratory measurements may be obtained at any time during the study to assess any perceived safety issues.

Safety assessments will include collection of AEs, SAEs, vital signs and physical examinations, ECG (12-lead), injection site examinations, laboratory assessments, including pregnancy tests and verification of concomitant treatments.

8.2.1. Participant Demographics and Other Baseline Characteristics

Demographic data and general medical history will be collected at screening by the investigator or qualified designee and will include relevant medical and surgical history within the last 10 years and current illnesses.

A disease-targeted medical and treatment history will be collected at screening. Details regarding the participant's malignancy under study, including date and stage at initial diagnosis, date and extent of metastatic disease at study entry, tumor histology and known gene alterations, relevant disease characteristics and prior anti-cancer treatments, including systemic, radiation and surgical procedures, will be recorded.

8.2.2. Physical Examinations

Participants will have a physical examination to include weight, vital signs, assessment of ECOG performance status, and height as per the [SoA](#).

A complete physical examination will include, at a minimum, assessments of the cardiovascular, respiratory, gastrointestinal, and neurological systems.

A brief physical examination will include, at a minimum, assessments of skin, lungs, cardiovascular system, and abdomen (liver and spleen).

Investigators should pay special attention to clinical signs related to previous serious illnesses.

Physical examinations may be conducted by a physician, trained physician's assistant, or nurse practitioner as acceptable according to local regulation.

Height and weight will also be measured and recorded as per the [SoA](#). For measuring weight, a scale with appropriate range and resolution is used and must be placed on a stable, flat surface. Participants must remove shoes, bulky layers of clothing, and jackets so that only light clothing remains. They must also remove the contents of their pockets and remain still during measurement of weight.

Physical examination findings collected during the study will be considered source data and will not be required to be reported, unless otherwise noted. Any untoward physical examination findings that are identified during the active collection period and meet the definition of an AE or SAE ([Appendix 3](#)) must be reported according to the processes in [Sections 8.3.1 to 8.3.3](#).

When should it be done:

Physical examination should precede blood draw for clinical laboratory tests.

